7.6.6 Other Analysis of Secondary Efficacy Endpoints

The analysis of efficacy of the above-mentioned endpoints (primary endpoint and secondary endpoints included in the hierarchical analysis) will be conducted at timepoints other than Week 6 in the DBPC Cycle and is described below (except urodynamic endpoints as only performed at Week 6). The analysis of other secondary endpoints (see Section 3.2) is also described below.

Descriptive summaries will be performed for the DBPC Cycle and by Dysport Cycles (i.e. Dysport Cycle 1, Dysport cycle 2 ...), see the schematic diagram in Section 7.1.

Statistical comparison analyses are only applicable for the DBPC treatment cycle. Analyses between treatment groups, Dysport 600 U vs. Placebo, and Dysport 800 U vs. Placebo will be performed accordingly using GLMM and MMRM as mentioned below for each endpoint. As all subjects should have visits up to and including week 12, but thereafter visits are dependent on whether the subject receives retreatment, statistical testing between treatment groups will be performed only up to Week 12, inclusive. All secondary endpoints not included in the hierarchical analysis are considered as exploratory endpoints and will therefore be analysed for exploratory purposes only to compare each Dysport dose to placebo, alpha at 0.05 level.

7.6.6.1 Diary Parameters

Refer to Section 3.2 for details of diary parameter endpoints.

7.6.6.1.1 Weekly Number of UI Episodes

Mean change from study baseline

For both the DBPC Cycle and the Dysport Cycles, summary tables for mean values in each assessment visit and the mean change from study baseline will be presented using descriptive statistics

For the DBPC treatment cycle, mean change from study baseline to Week 2, and Week 12, will also be analysed using MMRM, using data from Week 2, 6 and 12, as in the primary efficacy analysis in section 7.6.3.

Thresholds of reduction

For both the DBPC Cycle and the Dysport Cycles, the number and percentage of subjects with UI will be summarised by improvement levels from study baseline ($\geq 30\%$ improvement, $\geq 50\%$ improvement, $\geq 75\%$ improvement, 100% improvement (no episodes of UI)) for each assessment visit.

Bar charts will also be plotted. For the DBPC treatment cycle, the GLMM for repeated measures will be fitted for UI responses using repeated measurements at Week 2, Week 6, Week 12. Each UI response level compared to study baseline ($\geq 30\%$ improvement, $\geq 50\%$ improvement, $\geq 75\%$ improvement or 100%) will be analysed as a response variable in each model, as described for the proportion of subjects with no UI episodes in section 7.6.5.

7.6.6.1.2 Daily Urinary Frequency and Voided Volume

For both the DBPC Cycle and by Dysport Cycles, the summary tables for mean values in each assessment visit and the mean change from study baseline will be presented using descriptive statistics.

For the DBPC treatment cycle, mean change from study baseline to Week 2, Week 6, and Week 12 will be analysed using MMRM, as in the primary efficacy analysis presented in Section 7.6.4.2.

7.6.6.2 Urodynamic Filling Cystometry Parameters

See Section 3.2 for list of urodynamic endpoints.

The summary tables for mean values at Week 6 and the mean change from study baseline for the DBPC cycle, and for the Dysport Cycles (i.e. Dysport Cycle 1, Dysport cycle 2 ...) will be presented using descriptive statistics for continuous endpoints. For each of the “mean change” at Week 6 urodynamic parameters, an ANCOVA model will be fitted using the “mean change” endpoint, as the response variable to obtain the p-value of treatment groups. The model will be the same as the sensitivity analyses for the primary efficacy endpoint in 7.6.4.2. The LSMEANS of the mean change from study baseline at Week 6 in each group with standard error, the difference of mean between the two treatment groups, the 95% CI of the difference and the p-value for treatment group will be presented.

Number and percentage of subjects with no IDC will be also summarised. A logistic regression model will be performed with “proportion of subjects” as the response variable. The model will include treatment group, and stratification variables.

Odds ratio, 95% CI of odds ratio, and p-value will be presented.

The SAS codes of logistic regression for reference are below.

CCI
[Redacted SAS code block]

In above codes, the variables are defined as:

Statistical Analysis Plan

Version: Final v1.0

Date of Issue: 21-

September-2018

Ipsen Protocol No. D-FR-52120-223

Covance Study ID:

000000146513

CCI

Line plots of the LS means of changes will be plotted for MCC, MDP, Vol@1stIDC. In addition, a bar chart for the proportion of subjects with no IDC at Week 6 will be plotted.

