## Methodology:

### Study design

This is a phase III, multicentre, randomised, double blind, parallel group, placebo controlled study to assess the efficacy and safety of two Dysport® doses (600 U and 800 U) administered to the bladder of adult subjects with SCI or MS, and UI due to NDO.

PAGE 6/139

This study has two treatment periods:

- A double blind placebo controlled period, during which subjects receive a single IMP treatment administration of either 600 U or 800 U Dysport® or placebo.
- A subsequent double blind active treatment period, during which subjects can receive multiple active IMP retreatment administrations of either 600 U or 800 U Dysport®.

The study contains two subsets:

- Urodynamic subset (planned ≥200 subjects)
  - All subjects in this subset must have standardised urodynamics (as described in the Study Specific Urodynamic Manual) during Screening and at Week 6 following each study treatment
  - o Screening standardised urodynamics must confirm the presence of NDO
- Non-Urodynamic subset
  - All subjects in this subset must have documented urodynamic proven NDO in the 12 months prior to Screening. If not, then urodynamics must be performed per local practice during Screening to confirm the diagnosis of NDO
  - Urodynamics will not be performed in the post-screening period in this subset

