## 7.3.2 Urodynamic Examination

#### 7.3.2.1 Subjects in the Urodynamic Subset

Subjects in the urodynamic subset will undergo a standardised urodynamic (filling cystometry) assessment at Screening and again at Week 6 following each IMP administration.

Urodynamics will be conducted according to International Continence Society recommendations [20]. Full details of the urodynamic procedures including standardisation, training, equipment setup, subject preparation, trace annotations, calculations and central review process are contained in a separate Study Specific Urodynamic Manual.

All urodynamic procedures will be covered with a minimum of 2 days of appropriate prophylactic antibiotics. See Section 6.4.1.2 for further details on antibiotic prophylaxis in the study.

All urodynamic data will be reviewed by independent central reviewers to determine the final values for the urodynamic parameters. The central reader's determination will be used for analysis purposes.

During Screening the site will determine if the subject has NDO via the presence of IDCs (inclusion criterion #16); without confirmation from the central reader.

The following urodynamic parameters will be obtained (Table 20):

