7.6.3 Primary Efficacy Analysis

The primary efficacy endpoint is mean change in the weekly number of UI episodes from study baseline to Week 6 after the first treatment. Seven-day bladder diaries that contain data recorded on at least 5 days will be included in the analysis.

As all subjects should have visits up to and including week 12, but thereafter visits are dependent on whether the subject receives retreatment, statistical testing between treatment

Statistical Analysis Plan

Version: Final v1.0

September-2018

Ipsen Protocol No. D-FR-52120-223

000000146513

Date of Issue: 21-

Covance Study ID:

groups will be performed only up to Week 12, inclusive. Descriptive statistics table will present any timepoint.

Weekly number of UI episodes and the mean change from study baseline will be presented for the DBPC Cycle. The mixed model repeated measures (MMRM) analysis will be conducted with the change of the weekly number of UI episodes from study baseline as response variable. Fixed effect variables include treatment group, visit (Week 2, Week 6 and Week 12), treatment-by-visit interaction, stratification variables [the aetiology of NDO and prior intradetrusor BTX-A usage for UI] and study baseline value of weekly number of UI episodes. Random effect will include the subject effect. An unstructured covariance matrix will be specified in the mixed model to account for within subject correlation. If model fails to converge, the structure of first order autoregressive AR (1), compound symmetry (CS) or variance components (VC) will be used.

The least square means (LSMEANS) of the change of weekly number of UI at each visit in each group with standard error, the difference of mean between the two treatment groups at each visit, the 95% CI of the difference and the p-value for treatment group will be presented. The comparison of main interest will be treatment difference at Week 6.

The SAS codes of MMRM for reference are below.

CCI
[Redacted SAS code]

The validity of the model assumptions of normality will be investigated using residual plots. The LS means of change from study baseline for weekly UI in the DBPC and Dysport Cycles will be presented in line plots by treatment groups.

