7.6.5 Hierarchical Analysis of Secondary Efficacy Endpoints

As specified in Section 7.6.12, a hierarchical analysis will be performed in the order listed for the following two secondary efficacy endpoints at Week 6 after the first IMP administration:

- 1) Proportion of subjects with no episodes of UI (i.e. continence is achieved)
- 2) Mean change from study Baseline in the I-QoL total summary score

The Derivation rules are specified in Section 3.2 and Appendix II.

For 1), a logistic generalised linear mixed model (GLMM) for repeated measures will be fitted for UI responses using repeated measurements at Week 2, Week 6, and Week 12. The “proportion of subjects with no episodes of UI” will be analysed as a response variable, the model will include treatment group, stratification variables, study baseline value, visit (week 2, week 6 and week 12), study baseline*visit and treatment*visit interactions as fixed effect. The study baseline value will be weekly number of UI episodes. The logistic GLMM is fitted using the logit link and the binomial distribution. Odds ratios, 95% CIs of odds ratio, and p-values for treatment group comparisons at each visit (week 2, week 6 and week 12) will be presented.

The SAS codes of GLMM for reference are below.

CCI [redacted]
 [redacted]
 [redacted]
 [redacted]
 [redacted]
 [redacted]
 [redacted]
 [redacted]
 [redacted]

In above codes, the variables are defined as:

CCI [redacted]
 [redacted]

CCI

For 2), MMRM model will be fitted using the “mean change” endpoint, as the response variable to obtain the p-value of treatment groups. The model will be the same as primary analysis model in section 7.6.3. The least square means of change at Week 6 in each group with standard error, the mean difference of pairwise comparison, the 95% CI of the difference and the p-value for the treatment groups will be presented for each model.

If the testing procedure is stopped at the end of any particular step, the outcomes of the following steps will be presented and used for description only and no formal statistical conclusion will be drawn.

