For the DBPC Cycle for I-QOL and EQ-5D-5L, mean change from study baseline to Week 6 and Week 12, will be analysed using MMRM, similar to the primary efficacy analysis. Mean mPGI-I score at Week 2, Week 6, Week 12 will be analysed as a response variable, using MMRM as in the supportive primary analysis, without baseline factor for mPGI-I.

The LS means of change from study baseline in DBPC cycle for I-QoL total summary score at all timepoints will be presented in a line plot by treatment groups up to Week 12.

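### The no-IDC logistic model and the mPGI-I MMRM adjust for the two stratification factors but for no baseline severity measure; adding one already collected would be a small, nearly free gain

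*SAP*

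**What the plan says.** **No-IDC (SAP 7.6.6.2).** A logistic regression at Week 6 in the urodynamic population, reported as an odds ratio with 95% CI and p-value. On covariates: "The model will include treatment group, and stratification variables".

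**mPGI-I (SAP 7.6.6.3).** The mean score at Weeks 2, 6 and 12 is analysed "using MMRM as in the supportive primary analysis, without baseline factor for mPGI-I". The model it borrows is the one in SAP 7.6.3: "Fixed effect variables include treatment group, visit (Week 2, Week 6 and Week 12), treatment-by-visit interaction, stratification variables", followed by the study baseline of weekly UI episodes. Without the baseline term, treatment, visit, their interaction and the two strata remain.

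**Other models in the same SAP.** The continence model (7.6.5) lists "stratification variables, study baseline value, visit (week 2, week 6 and week 12" and adds: "The study baseline value will be weekly number of UI episodes". The UI responder thresholds (7.6.6.1.1) reuse it. The continuous urodynamic changes use the ANCOVA of 7.6.4.2, which carries a study baseline term.

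**Status.** SAP 7.6.2 and 7.6.6 class everything outside the two-endpoint hierarchy as exploratory, at 0.05. Protocol 9.6 places the no-IDC proportion fourth in a separate urodynamic hierarchy.

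**The concern.** Every subject keeps a Screening bladder diary, so baseline weekly UI is available for mPGI-I, which asks the subject to rate change in UI (Protocol 7.3.3.3). Every subject in the urodynamic subset has standardised Screening urodynamics, with central review of the traces (Protocol 7.3.2.1), so a baseline MCC, MDP or Vol@1stIDC should be available for no-IDC. If these baselines predict outcome, leaving them out forgoes some power or precision that needs no new data.

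The continence model is the useful precedent. Entry requires an average of at least two UI episodes per day (Protocol 4.1, criterion 14), so nobody is continent at baseline and the binary endpoint has no baseline variation of its own. The SAP adjusts for the severity behind it. No-IDC is in much the same position, but its model gets no severity term.

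What is at stake is modest: some power for an endpoint that the protocol ranks, in a subset planned at about 67 per arm, and some precision for mPGI-I.

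**Working it through.** **Inputs from the documents.** Urodynamic subset at least 200 (Protocol 9.6). 330 randomised and 10% dropout to Week 6 (SAP 2.3). Allocation 2:2:1:1 with placebo pooled, so 1:1:1 for Treatment 1 (Protocol 3.3.1). Two-sided 5% tests (Protocol 9.3). This gives 200/3 ≈ 67 per arm in the subset and 330 × 0.9/3 = 99 per arm for mPGI-I.

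**Assumed, because neither document gives them.** No-IDC rates, the odds ratio per SD of the baseline covariate, and the correlation r between baseline UI and mPGI-I.

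**Step 1: the plan's own figure.** The only urodynamic power statement is Protocol Table 21: 200 subjects, 90% power for MCC, difference 104.5 mL, SD 212.9 mL. With k Dysport subjects per placebo subject, placebo n = (1 + 1/k)(1.960 + 1.282)² (212.9/104.5)² = (1 + 1/k) × 10.51 × 4.151 = (1 + 1/k) × 43.6.

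- k = 2 (pooled Dysport): 65.4, so 66 + 132 = 198. The stated 200 reproduces (power 90.5%).
- k = 1 (one dose against placebo): 87.2, so 88 per arm. At 67 per arm power is 80.9%.

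No covariate enters this formula, so it neither supports nor contradicts the point. No figure is given for no-IDC or mPGI-I.

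**Step 2: mPGI-I.** For a linear model at one visit, a covariate with partial correlation r multiplies the residual variance by 1 − r². The last column starts from a notional 80% at 99 per arm.

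| r | variance reduction | SE factor √(1 − r²) | effective sample size | power from 80% |
|---|---|---|---|---|
| 0.1 | 1% | 0.995 | +1% | 80.4% |
| 0.2 | 4% | 0.980 | +4% | 81.6% |
| 0.3 | 9% | 0.954 | +10% | 83.6% |
| 0.4 | 16% | 0.917 | +19% | 86.4% |

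**Step 3: no-IDC.** Simulated logistic regressions, 67 per arm, 3,000 runs per row, Wald tests, with and without one standardised baseline covariate. The strata were left out of both models, so the covariate's strength should be read as additional to them. Simulation error on each power is about √(0.8 × 0.2/3000) = 0.7 points.

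| Rates | OR per SD | power without | power with | SE ratio, log OR |
|---|---|---|---|---|
| 10% v 30% | 1.0 | 84.2% | 84.6% | 1.007 |
| 10% v 30% | 1.5 | 83.4% | 84.6% | 1.022 |
| 10% v 30% | 2 | 84.5% | 87.2% | 1.049 |
| 10% v 30% | 3 | 83.1% | 88.3% | 1.115 |
| 20% v 40% | 1.0 | 72.8% | 72.5% | 1.009 |
| 20% v 40% | 1.5 | 71.4% | 71.7% | 1.028 |
| 20% v 40% | 2 | 72.0% | 75.3% | 1.065 |
| 20% v 40% | 3 | 71.6% | 79.9% | 1.137 |

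The SE of the log odds ratio rises in every row. Power rises with a prognostic covariate because the estimate moves further from zero: at 20% v 40% and OR 3, from 0.997 to 1.233. On a standardised risk-difference scale the empirical SE does fall, by about 1% to 9% for OR 1.5 to 3. At 60 per arm (67 less 10%) with 15% v 33%, likelihood-ratio tests gave 66% to 69% at OR 2 and 66% to 73% at OR 3.

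**The case against.** The best defence is that the SAP adjusts for an endpoint's own baseline where one exists, and these two have none. For no-IDC, "Screening standardised urodynamics must confirm the presence of NDO", and "During Screening the site will determine if the subject has NDO via the presence of IDCs", so the baseline status hardly varies. mPGI-I rates change since the last treatment and cannot have a baseline. Continence, by contrast, is derived from the UI count it is adjusted for. This explains the omission. It does not bar a related severity measure, which is what the continence model uses. It does mean that choosing MCC is a judgement: Vol@1stIDC or MDP are equally available, and nothing in the documents favours one.

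Three stronger readings are tempting, and the documents do not support them.

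- **That the models have no baseline covariates.** Both keep aetiology and prior BTX-A use. Only a severity term is absent.
- **That precision is being lost for no-IDC.** The planned output is an odds ratio, whose SE on the log scale rises with adjustment. Any gain is in power, and the estimand becomes conditional on the covariate.
- **That a loss is demonstrated.** No prognostic strength is given anywhere. With a non-prognostic covariate the simulated change is within simulation error.

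Two textual limits also stand. The mPGI-I phrase may mean only that the non-existent mPGI-I baseline is removed, and the supportive primary analysis it cites is unclear, since SAP 7.6.4.1 uses that adjective for the per-protocol analysis. The logistic SAS code is blacked out, so a further term there cannot be ruled out; the point rests on the readable model statement.

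**Conclusion.** The point holds as a minor improvement. As written, the two models contain no baseline severity covariate beyond the strata, while comparable models in the same SAP do. The unadjusted tests remain valid, both endpoints are exploratory in the SAP, and no primary or key secondary conclusion is touched. The protocol's ranking of no-IDC makes the change somewhat more worthwhile but does not turn the omission into an error.

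The size is conditional. For mPGI-I, variance falls by r squared and the gain is slight unless r exceeds about 0.2. For no-IDC, power rises by about 0 to 8 points over assumed odds ratios of 1 to 3 per SD, with little or nothing at 1.5. The downside of a non-prognostic covariate is negligible, provided that a missing baseline does not remove subjects from the model.

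**What to change.** - **SAP 7.6.6.3.** State that the mPGI-I MMRM includes baseline weekly number of UI episodes as a covariate, and cite the intended model by section number (7.6.3). This also settles the ambiguity about which term is dropped.
- **SAP 7.6.6.2.** Add one prespecified, centrally read baseline urodynamic value, for example MCC, to the no-IDC logistic model. State that the odds ratio is then conditional on it. Give a simple rule for a missing baseline, for example the mean over all arms of the urodynamic population, so that no subject is lost.

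The cost is a few phrases in a SAP amendment before database lock, which SAP section 1 allows for. No new data are needed.

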7.6.6.3 Patient Reported Outcome Questionnaires

This includes the I-QOL, EQ-5D-5L and mPGI-I endpoints (see Section 3.2).

EQ-5D-5L comprises of the descriptive system for 5 dimensions: mobility, self-care, usual activities, pain/discomfort and anxiety/depression, where each dimension has 5 levels (1=indicating no problem, 2=indicating slight problems, 3=indicating moderate problems, 4=indicating severe problems, 5=indicating extreme problems). It also includes a self-rated health which is numbered from 0 (worst health you can imagine) to 100 (best health you can imagine):

Level	Mobility	Self-care	Usual Activities	Pain/Discomfort	Anxiety/Depression
1	I have no problems walking,	I have no problems washing or dressing myself	I have no problems doing my usual activities	I have no pain or discomfort	I am not anxious or depressed
2	I have slight problems walking,	I have slight problems washing or dressing myself	I have slight problems doing my usual activities	I have slight pain or discomfort	I am slightly anxious or depressed
3	I have moderate problems walking,	I have moderate problems washing or dressing myself	I have moderate problems doing my usual activities	I have moderate pain or discomfort	I am moderately anxious or depressed
4	I have severe problems walking,	I have severe problems washing or dressing myself	I have severe problems doing my usual activities	I have severe pain or discomfort	I am severely anxious or depressed
5	I am unable to walk	I am unable to wash or dress myself	I am unable to do my usual activities	I have extreme pain or discomfort	I am extremely anxious or depressed

Statistical Analysis Plan

Version: Final v1.0

September-2018

Ipsen Protocol No. D-FR-52120-223

000000146513

Date of Issue: 21-

Covance Study ID:

The EQ-5D-5L descriptive system will be added numerically e.g. mobility=2, self-care=3, usual activities=2, pain/discomfort=3, anxiety/depression=2 gives a state=23232 i.e. slight problems with mobility, moderate problems with washing or dressing, slight problems with doing usual activities, moderate pain or discomfort, and slightly anxious or depressed. Missing values will be coded as a 9. The arithmetic score for the EQ-5D-5L score will be taken as $2+3+2+3+2=12$.

For both the DBPC Cycle and by the Dysport Cycles, the summary tables for mean values in each assessment visit and the mean change from study baseline will be presented using descriptive statistics.

For the DBPC Cycle for I-QOL and EQ-5D-5L, mean change from study baseline to Week 6 and Week 12, will be analysed using MMRM, similar to the primary efficacy analysis. Mean mPGI-I score at Week 2, Week 6, Week 12 will be analysed as a response variable, using MMRM as in the supportive primary analysis, without baseline factor for mPGI-I.

The LS means of change from study baseline in DBPC cycle for I-QoL total summary score at all timepoints will be presented in a line plot by treatment groups up to Week 12.

7.6.6.4 Retreatment intervals

For both the DBPC Cycle and by the Dysport Cycles, summary statistics will be displayed for time between treatments received, time to request and time to eligibility for retreatment. For the DBPC Cycle the number and percentage of patients receiving retreatment: \geq Week 12 to $<$ Week 16, \geq Week 16 to $<$ Week 20 weeks and then every 4 weeks will be presented.

The following formal statistics will be performed only for the time between treatments received endpoint. For both the DBPC Cycle and by the Dysport Cycles, median number of days together with the 25th and 75th percentiles and their 95% CI will be determined based on the Kaplan-Meier method. Patients with no retreatment will be censored at the last visit. The survival curves will be presented by treatment group as well.

For the DBPC and Dysport treatment cycles, the log-rank tests will be performed to compare survival curves between treatment groups, by providing p-values.

The SAS codes of survival analysis for reference are below.

CCI

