#### 9.4.5 Efficacy Evaluation

As indicated in Section 7.1, the primary efficacy variable is the change in the weekly number of UI episodes from Baseline (Day 1) to Week 6 after the first treatment.

Secondary efficacy variables are:

- weekly number of UI episodes
- proportion of subjects with no episodes of UI
- I-QoL total summary score (as well as individual domain scores i.e. avoidance and limiting behaviour, psychosocial impact, and social embarrassment)
- urinary frequency (total, spontaneous only, CIC only)
- 24-hour voided volume (total, spontaneous only, CIC only)
- volume per void (total, spontaneous only, CIC only)
- EQ-5D-5L score
- mPGI-I score
- proportion of subjects with UI response at several levels (i.e. ≥30% improvement, ≥50% improvement, ≥75% improvement, etc.)
- time to retreatment request
- time to eligibility for retreatment
- time between treatments.

Efficacy assessments performed only in the urodynamic population are described in Section 9.6.

Full details of these assessments and timings are given in Section 7.2.

The study Baseline value will be defined as the last value available prior to the first study IMP treatment administration.

The aetiology of NDO (SCI or MS) and prior intradetrusor BTX-A usage for UI (BTX-naive and BTX-non-naive) will be used as covariates in the primary model. The results of the treatment effect will be presented for each subgroup formed by the covariates (see Section 9.5 for further details). In order to assess the impact of missing data on the conclusion of the primary analysis, a sensitivity analysis of the primary efficacy endpoint will be performed using a multiple imputation approach.

If the parametric assumptions of the analysis are not satisfied, then a suitable transformation or a nonparametric procedure will be sought.

Secondary efficacy endpoints will be assessed according to their scale (categorical or continuous), using a logistic regression model, mixed model, or survival analysis-type methods (e.g. Kaplan-Meier plots, log-rank statistics).

Time to event data will be analysed by using survival methods. The results will be presented both in summary tables and graphically in Kaplan-Meier plots.

Responders defined as subjects having an improvement in UI will be presented at several levels (i.e.  $\geq$ 30% of improvement,  $\geq$ 50% of improvement,  $\geq$ 75% of improvement, etc.) for exploratory purposes.

PAGE 106/139

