7 STATISTICAL METHODS

7.1 General Principles

All data processing, summarisation and analyses will be performed using the SAS Environment / Version 9.4 (or later) of the SAS[®] statistical software package.

All data collected during the study will be presented in listings without any imputation by treatment group, subject, assessment and visit (where applicable), unless otherwise specified.

Data will be presented in summary tables by treatment group (as described below), assessment and visit (where applicable).

Overall, the analysis strategy is to evaluate efficacy and safety data from the initial DBPC Cycle and to evaluate efficacy and safety over repeated Dysport treatments, using analyses by Dysport Cycle (Dysport Cycle 1, 2...etc.), as illustrated in schematic diagram later in this section. In general, tables associated with the DBPC Cycle will be separate from the tables assessing repeat treatment with Dysport which are presented by Dysport Cycle:

- During analysis of the DBPC (DBPC cycle), data will be displayed using the following treatment group labels, in the order presented:
 - Placebo
 - Dysport 600 U
 - Dysport 800 U
 - All Dysport
- During analysis by Dysport Cycle, data will be displayed by number of Dysport treatments (see diagram below) using the following treatment group labels:
 - Dysport Cycle 1
 - Dysport 600U
 - Dysport 800U
 - All Dysport
 - Dysport Cycle 2
 - Dysport 600U
 - Dysport 800U
 - All Dysport
 - Dysport Cycle X

Statistical Analysis Plan

Version: Final v1.0
September-2018
Ipsen Protocol No. D-FR-52120-223
000000146513

[figure not shown]
Date of Issue: 21-
Covance Study ID:

- Dysport 600U
- Dysport 800U
- All Dysport

Analysis of Dysport Cycle 1 will therefore include (see diagram below):

- Data from subjects who received a Dysport treatment after having initially received placebo as their first study treatment on Day 1 i.e. will only use data from their first Dysport treatment,
- Data from subjects who received Dysport as their first study treatment on Day 1

Schematic diagram summarising concept of Dysport Cycles:

Descriptive summary statistics for continuous variables will include the number of subjects (n), mean, standard deviation (SD), median, minimum and maximum.

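### The SAP gives survival analysis to only one of the three retreatment intervals, although the protocol plans it for time-to-event data without exception, and declares no change

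*SAP*

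**What the plan says.** Protocol 9.4.5 names three retreatment intervals among the secondary efficacy variables: "time to retreatment request", time to eligibility and time between treatments. They are the only time-to-event variables in that list. The same section says "Time to event data will be analysed by using survival methods" and "The results will be presented both in summary tables and graphically in Kaplan-Meier plots". It makes no exception for any interval.

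SAP 3.2 keeps all three as measures of duration of effect. In SAP 7.6.6.4, "summary statistics will be displayed for time between treatments received, time to request and time to eligibility for retreatment", for the placebo-controlled cycle and for each Dysport cycle. The section then states: "The following formal statistics will be performed only for the time between treatments received endpoint". Those formal statistics are Kaplan-Meier quartiles with confidence intervals, survival curves and log-rank tests. The one censoring rule given there is "Patients with no retreatment will be censored at the last visit".

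SAP 7.1 explains what plain summaries contain: "Descriptive summary statistics for continuous variables will include the number of subjects (n), mean, standard deviation (SD), median, minimum and maximum". SAP Section 8, which is the place for departures from the protocol's analyses, records none.

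**The concern.** Two of the three measures of duration of effect lose the method that Protocol 9.4.5 assigns to time-to-event data, and the SAP does not record this as a change.

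The omitted method is the one that handles censoring. A subject who has made no qualifying request, or has not been confirmed eligible, by the end of follow-up at Week 104 to 116 has no event time. The same holds at the data cut-off used for the primary analysis (SAP 7.8). A mean or median cannot include such a subject without a further rule. If these subjects are dropped, the summary describes only those whose effect wore off within the observation period. It then understates duration, and more so in an arm with a longer effect, so differences between arms shrink.

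Duration of effect is named in two of the secondary objectives (Protocol 2.2). The SAP is also inconsistent within itself. SAP 7.6.2 says every secondary endpoint outside the hierarchy will be compared with placebo on an exploratory basis, but 7.6.6.4 gives these two no comparison.

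**Working it through.** **Comparison of the texts.** The plan gives no figure to reproduce, so the first check is a count.

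| Interval | Protocol 9.4.5 | SAP 7.6.6.4 |
|---|---|---|
| Time to request | survival methods, Kaplan-Meier plot | summary statistics only |
| Time to eligibility | survival methods, Kaplan-Meier plot | summary statistics only |
| Time between treatments | survival methods, Kaplan-Meier plot | summary statistics, Kaplan-Meier, log-rank |

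Three intervals are planned for survival analysis, one receives it, and Section 8 declares no change.

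**Illustration of size.** Inputs from the documents: retreatment cannot be requested before 12 weeks (Protocol 5.2.5), and retreatments can occur up to Week 104 (Protocol 3.4). Assumptions not in the documents: first cycle only, complete follow-up to Week 104, event time T = 12 weeks plus a Weibull time with shape k, and subjects without the event left out of the summary.

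For a true median m:

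- Proportion without the event: S = 2^−[(92/(m − 12))^k], where 92 = 104 − 12.
- The median among observed events, t, solves F(t) = F(104)/2, so t = 12 + (m − 12) × [−log2((1 + S)/2)]^(1/k).

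Example with k = 1 (exponential) and m = 60: S = 2^−(92/48) = 0.265; (1 + 0.265)/2 = 0.632; −log2(0.632) = 0.661; t = 12 + 48 × 0.661 = 43.7 weeks.

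| Shape k | True median (weeks) | Without event | Median among observed events |
|---|---|---|---|
| 1 | 30 | 2.9% | 29.3 |
| 1 | 40 | 10.3% | 36.1 |
| 1 | 60 | 26.5% | 43.7 |
| 1.5 | 30 | 0.0% | 30.0 |
| 1.5 | 40 | 1.6% | 39.6 |
| 1.5 | 60 | 15.9% | 52.9 |

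For arms with true medians of 40 and 60 weeks, the true gap is 20. From unrounded values it reads as 7.7 weeks with k = 1 and 13.4 with k = 1.5. A simulation of 2,000,000 subjects for k = 1 gave 29.2, 36.1 and 43.7.

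With less spread the bias fades. With k = 2 a true median of 60 reads 57.3, and with k = 3 it reads 59.8. At a true median of 20 weeks there is none for shapes from 1 to 3.

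**The case against.** The strongest reply is that the protocol's endpoint-specific text is met. Section 9.4.5 refers to Section 7.2 for details, and Table 19 there defines each interval as a mean and median number of days, counting a request only if the subject is later found eligible. The SAP's summaries deliver that, and the survival sentence in 9.4.5 names no interval. But Table 19 words all three intervals in the same way, and the SAP still gives one of them Kaplan-Meier, so Table 19 does not explain the different treatment. A Kaplan-Meier median would satisfy Table 19 as well.

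Other points stand in part:

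- **Little may be lost.** The assessment visit ideally falls within 14 days of the request, and retreatment within 14 days of confirmed eligibility. When both targets hold, the first and last intervals differ by at most about 28 days, and the last has a censored analysis. The targets are not binding, however, and the protocol chose to measure the earlier steps separately.
- **The restriction is open and prespecified.** That is so. What is missing is its declaration as a change.
- **Bias is not shown.** Appendix II, which holds the endpoint definitions, is withheld and may say how subjects without the event are handled. This stands: the mismatch between the documents is certain, the bias is conditional.
- **The size depends on the assumed shape.** This also stands. A material bias needs both a long median and a wide spread.
- **The endpoints are exploratory.** The primary result, the hierarchical tests and type one error control are untouched.

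**Conclusion.** The concern holds. SAP 7.6.6.4 departs from Protocol 9.4.5 for two of three duration-of-effect endpoints, and Section 8 does not say so. This rests on the text alone.

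The consequence for the estimates is conditional on subjects without the event being left out. Under the assumptions above, the understatement at a true median of 60 weeks runs from about 16 weeks (60 − 43.7, exponential) to about 7 (60 − 52.9, shape 1.5), and to almost nothing for tighter distributions. At 30 weeks it is below 1 week throughout. An early cut-off for the primary analysis could make it larger, but the cut-off text is redacted.

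The impact is modest. The change should be made because the plan already contains the better method and need only apply it.

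**What to change.** In SAP 7.6.6.4, extend the planned Kaplan-Meier analysis (median, quartiles, 95% confidence intervals, curves) to time to request and time to eligibility. Unless Appendix II already has such a rule, censor subjects with no qualifying request, or no confirmed eligibility, at the last visit, or at the last visit before the cut-off. Because a request counts only once eligibility follows, the rule should also say which of several requests sets the event date and how a request still under assessment at the cut-off is treated.

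Keep the Table 19 means and medians, labelled as describing subjects with the event. A log-rank test for each interval is not needed, since the protocol offers it only as an example; if it is omitted, note the exception to the general comparison rule in SAP 7.6.2.

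If the restriction is intended, declare it in SAP Section 8 and state how subjects without the event enter the summaries.

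The cost is SAP wording, one censoring rule if Appendix II lacks it, and two more runs of a program already planned.
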